6.2 Observation and handling of adverse events

In this study, all subjects should undergo regular safety assessments, including subjective patient reports (such as abdominal pain, bloating), blood pressure, ultrafiltration volume, urine output, Nt-pro BNP, Kt/V, Ccr, PET, and other indicators. Researchers should document all adverse events that occur during the clinical trial and observe and manage them. The principles of inspection and handling are as follows:

The investigator should ask the subject if he or she feels any discomfort and actively observe whether the subject has any abnormal symptoms present.

Researchers should record the name, time of occurrence, duration, severity, and trial of all adverse events information such as causality, treatment measures and outcomes of the drug should be filled in the adverse event report form.

Researchers should provide appropriate treatment and support measures according to the nature and severity of adverse events closely monitor the subject's condition.

Researchers should decide whether to continue use based on the causal relationship and impact of adverse events and trial drugs. The test drug or withdrawal from the study.

Researchers should report all adverse events that occur during clinical trials to the ethics committee and sponsor in a timely manner events and track and update them as required.

6.3 Criteria for judging the relationship between adverse events and tests

The causal relationship between adverse events and the test drug should be judged according to the following criteria:

Assured of relevance (Definitely Related): Adverse events are related to the pharmacological action of the investigational drug or a known adverse event

The results were consistent and other possible causes were ruled out.

Most likely related (Probably Related): Adverse event and pharmacological action of the investigational drug or known no The good response is consistent and other possible causes are unlikely.

May be related (Possibly Related): Adverse event is related to the pharmacological action of the investigational drug or a known adverse eventThere are some similarities in the reaction, but there are other possible reasons.

It is unlikely to be related (Unlikely Related): the adverse event is related to the pharmacological action of the investigational drug or is known. There was no clear similarity in the adverse reactions and there were other more likely causes.

Irrelevant (Not Related): The adverse event is completely unrelated to the pharmacological action of the test drug or a known adverse reaction. It does not match and there are other clear reasons.

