6.5 Reporting of adverse events

All adverse events occurring during clinical trials shall be reported in accordance with the following requirements:

All adverse events should be filled in the adverse event report form within 24 hours after occurrence and 7 days after occurrence and report to the ethics committee and sponsor within days. All serious adverse events should be reported by telephone, fax, email, etc. within 24 hours after occurrence. Notify the ethics committee and the sponsor, and submit a written report within 7 days after the occurrence. All serious unexpected reactions (Serious Unexpected Adverse Reaction, SUSAR) related to the test drug should be reported to the National Food within 24 hours of occurrence by telephone, fax, email, etc. The drug administration shall submit a written report within 15 days after the occurrence. All serious unexpected adverse reactions unrelated to the test drug should be reported by telephone, fax or electronic means within 7 days of occurrence. Report to the State Food and Drug Administration by mail, etc., and submit a written report within 30 days after the occurrence.

7. Statistical considerations

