7.6.3 Statistical analysis of secondary endpoints

Based on the EAS dataset, descriptive analysis will be used to summarize the baseline characteristics of enrolled subjects, changes in nutritional status, metabolic state, residual renal function, and trends in dialysis adequacy at 3 months and 6 months post-treatment, with graphical presentations. For the comparison of changes from baseline: continuous variables will be compared using paired t-tests or Wilcoxon-signed rank tests based on data distribution; for categorical variables, McNemar-tests will be used compare yourself before and after.

7.6.4 safety analysis

Based on the SS set, all AE will be summarized by descriptive analysis. In addition, they will be summarized separately by drug correlation, drug-related treatment measures, outcomes and severity. If necessary, they will be summarized by subgroup (e.g

Data were stratified according to whether dialysis was adequate or heart failure).

Summarize the changes of vital signs, laboratory tests and ECG results of each group relative to baseline, the results with clinical significance after baseline and all test results were listed.

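### The causality scale in 6.3 makes resemblance to known pharmacology or known reactions a condition of every related grade, so an unfamiliar event with no other cause has no grade

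*Combined protocol and SAP*

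**What the plan says.** Section 6.3 defines five classes, each joining a condition on resemblance to a condition on other causes.

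- Definitely related: "Adverse events are related to the pharmacological action of the investigational drug or a known adverse event", continued as "The results were consistent and other possible causes were ruled out".
- Probably related: the same consistency, with other causes improbable. The translation is broken here: "The good response is consistent and other possible causes are unlikely".
- Possibly related: some similarity, with other possible causes present.
- Unlikely related: "There was no clear similarity in the adverse reactions and there were other more likely causes".
- Not related: "It does not match and there are other clear reasons".

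There is no class for an event that cannot be assessed. Time to onset, response to stopping and recurrence on restarting appear in none of the five definitions.

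Other sections use the grade:

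- 6.2, on continuing the fluid: "Researchers should decide whether to continue use based on the causal relationship and impact of adverse events and trial drugs".
- 6.4, whose severity criteria are written only for events related to the investigational drug.
- 6.5, on expedited reporting: "All serious unexpected reactions (Serious Unexpected Adverse Reaction, SUSAR) related to the test drug should be reported to the National Food". The clock is 24 hours with a written report in 15 days; serious unexpected events judged unrelated have 7 and 30 days.
- 7.6.4, on analysis: after all adverse events are summarised, "they will be summarized separately by drug correlation, drug-related treatment measures, outcomes and severity".

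Section 6.1 is broader than 6.3. It accepts as an adverse reaction a harm caused by the drug's pharmacology or by something else about the drug. It reserves the unrelated category for events shown scientifically to have no causal link.

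**The concern.** The trial has no control group (3.1), so event rates on the amino acid fluid cannot be set against rates in a concurrent arm. Attribution of harm to the fluid then rests largely on grading individual events, and safety is one of the secondary objectives (2.2). A scale that can call an event related only if it looks like something already known works against finding what is not yet known. The SUSAR category in 6.5 exists for reactions that are unexpected, yet under 6.3 the only way an unexpected event can be graded related is by fitting the known pharmacology. An event that began after each amino acid bag and cleared without it could not be graded related on that evidence.

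**Working it through.** The plan gives no figure on this point, so the check is whether the five definitions cover the cases an investigator can meet.

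**Inputs.** From the wording of 6.3, resemblance takes 4 levels: consistent, some similarity, no clear similarity, no match. Other causes take 5 levels: ruled out, unlikely, possible, more likely, clear. That gives 4 × 5 = 20 combinations. The levels are my ordering of the plan's own terms.

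**Strict reading.** Each class occupies only the pair it names: consistent/ruled out, consistent/unlikely, some similarity/possible, no clear similarity/more likely, no match/clear. That is 5 of 20.

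**Lenient reading.** Stronger evidence is allowed to satisfy a weaker wording:

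| Resemblance | Ruled out | Unlikely | Possible | More likely | Clear |
|---|---|---|---|---|---|
| Consistent | Definitely, Probably | Probably | Possibly | Possibly | Possibly |
| Some similarity | none | none | Possibly | Possibly | Possibly |
| No clear similarity | none | none | none | Unlikely | Unlikely |
| No match | none | none | none | Unlikely | Unlikely, Not related |

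Filled: 5 + 3 + 2 + 2 = 12. Empty: 20 − 12 = 8. Six of the 8 lie in the two bottom rows, where the event resembles nothing known and no more likely cause has been found. The other two are events with some similarity and no plausible alternative, which meet neither the consistency needed for Probably nor the rival cause named in Possibly.

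**6.1 against 6.3.** Take an unfamiliar event with no other explanation. Under 6.1 it is not an unrelated event, because nothing has established the absence of a causal link, and the definition of a reaction does not confine it to known pharmacology. Under 6.3 it cannot be graded related, because resemblance is missing. It cannot be graded Unlikely or Not related either, because another cause is missing.

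**What follows downstream.**

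- 7.6.4: the event is in the table of all adverse events but has no proper place in the summary by drug relationship.
- 6.4: the severity criteria do not reach it, although 6.2 asks for severity to be recorded for every event.
- 6.5: if it is serious and unexpected, neither regulator clock clearly applies. Treated as unrelated, it gets 7 and 30 days in place of 24 hours and 15 days.

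**The case against.** The strongest reply is that little depends on the grade. Section 6.5 sends all adverse events to the ethics committee and sponsor within 7 days, and all serious ones within 24 hours, whatever their grade. Serious unexpected events judged unrelated still reach the regulator. Section 7.6.4 tabulates all adverse events, with drug relationship as an added breakdown. Section 6.2 has time of occurrence, duration and outcome recorded, so an event could be regraded later. The decision to continue the fluid also weighs impact, and 3.3.3 provides for withdrawal for life-threatening complications or on the investigator's assessment. The product is already marketed, and no primary result uses the grade. The text of 6.3 is also visibly damaged in translation.

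Most of this stands, and it limits the consequence. It does not fill the empty cells: both conditions can be read in all five classes despite the translation, and no class mentions timing.

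Three stronger readings are tempting and not supported.

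- A reader might infer that new reactions would be missed in expedited reporting and in the safety conclusion. Sections 6.2, 6.5 and 7.6.4 say otherwise. Item (17) of 4.1, which restricts collection to study-related events, could lose an event, but that is a separate contradiction with 6.2 and 6.5.
- A reader might infer that such events will be graded unrelated. That guesses at a forced choice; the text leaves them without a grade.
- A reader might apply an assumed incidence of unlisted reactions to the 140 patients. The documents give no such incidence, and the gap concerns only events that are also unlike the pharmacology and without a more likely cause.

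**Conclusion.** The gap holds on the wording of 6.3. Resemblance is necessary for every related grade, another cause is necessary for both remaining grades, and an event with neither has no grade. Even read leniently, 8 of 20 combinations are unclassified, 6 of them for events that resemble nothing known. That is a count of cells in the scale, not an estimate of how many patients would be affected, which the documents do not allow.

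The gap is narrower than all new harms. Every class also weighs other causes, and a new harm that fits the pharmacology can be graded related. The consequence is an incomplete or misattributed summary by drug relationship, no severity criteria for the event, and an undefined or slower clock to one recipient, the regulator. This is a wording correction worth making because the design has no comparator. It does not touch the primary analysis. The conclusion assumes that the translated text preserves the two conditions in each class.

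**What to change.** Reword 6.3 so that the grade is determined by three things: the time relationship to the fluid, the response to stopping or restarting where that information exists, and alternative causes. Let resemblance to known pharmacology or known reactions support a related grade without being required for one. Add one sentence: an event with a plausible time relationship and no more likely other cause is graded at least possibly related. Check the new definitions against a grid like the one above so that every combination has exactly one class.

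Align 6.3 with 6.1 in the same revision. Keep the five class names, so that the 7.6.4 tables need no change. Item (17) of 4.1 should be reconciled with 6.2 and 6.5 at the same time, as its own correction.

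The cost is protocol wording and investigator training. Somewhat more events will be graded possibly related. Any events already graded under the present wording would need review, for which the timing recorded under 6.2 should serve.

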6.4 Evaluation of adverse reactions

Adverse reactions (i.e., adverse events related to the investigational drug) should be evaluated according to the following criteria:

Mild (Mild): The adverse reaction is mild and does not affect the daily life and work of the subject, and no special treatment is required texture.

Moderate (Moderate): Moderate adverse reactions, affecting the daily life and work of subjects, requiring certain therapeutic or supportive measures.

Severe (Severe): The adverse reaction is serious and seriously affects the daily life and work of the subject, requiring urgent treatment rapid or specialized treatment or support measures.

6.5 Reporting of adverse events

All adverse events occurring during clinical trials shall be reported in accordance with the following requirements:

All adverse events should be filled in the adverse event report form within 24 hours after occurrence and 7 days after occurrence and report to the ethics committee and sponsor within days. All serious adverse events should be reported by telephone, fax, email, etc. within 24 hours after occurrence. Notify the ethics committee and the sponsor, and submit a written report within 7 days after the occurrence. All serious unexpected reactions (Serious Unexpected Adverse Reaction, SUSAR) related to the test drug should be reported to the National Food within 24 hours of occurrence by telephone, fax, email, etc. The drug administration shall submit a written report within 15 days after the occurrence. All serious unexpected adverse reactions unrelated to the test drug should be reported by telephone, fax or electronic means within 7 days of occurrence. Report to the State Food and Drug Administration by mail, etc., and submit a written report within 30 days after the occurrence.

7. Statistical considerations

7.1 Sample size calculation

This study is a post-marketing study, and a total of 140 subjects are planned to be included. The efficacy evaluation standard is 6 months of treatment

If the difference between the post-relative baseline change of Δ serum albumin or Δ prealbumin is statistically significant, it is considered

The treatment was effective. Based on the above hypothesis, a single sample self-preceding and following control design and a unilateral difference test were used

Quantity estimation formula:

$$n = \frac{(z_{\alpha} + z_{\beta}) \sigma^2}{\delta^2}$$

δ is the difference; σ is the standard deviation, which will be replaced by the sample size standard deviation.

The Hochberg method was considered to adjust for multiple endpoints, with the smallest test level $\alpha/2= 0.0125$ (one-sided) and power $(1- \beta) = 0.9$, based on the sample size estimates for different primary efficacy endpoints count.

1) Based on Δ serum albumin: According to the literature, it is assumed that the baseline serum albumin before treatment is 27 g/L, and the serum albumin after 6 months of amino acid peritoneal dialysis treatment is 28.5g/L, δ is 1.5g/L, and the standard deviation is 4.5 g/L,

The required sample size for the calculation was 112.

2) Based on Δ prealbumin: According to the literature, it is assumed that the baseline prealbumin before treatment is 240 mg/L, the prealbumin 6 months after amino acid peritoneal dialysis treatment is 300mg/L, δ is 60mg/L, and the standard deviation is 80 mg/L, the required sample size for calculation is 23 cases.

In order to ensure that the final analysis of this study has enough sample size, considering the possible loss to follow-up, withdrawal, invalid data and other situations, the maximum sample size of 112 cases estimated based on the above two indicators will be increased by 20%

The dropout rate was expanded to a total sample of 140 cases.

7.2 analysis set

7.4 General analysis considerations

Continuous variables will be statistically described based on the data distribution, including number of cases (non-missing numbers), mean, standard deviation, median and quartiles, maximum value, and minimum value. For categorical variables, the number of cases and percentages for each category will be calculated unless otherwise specified; missing cases will not be included in percentage calculations, and counts with zero cases will be displayed as "0". The distribution of participants, demographic characteristics, past medical history/comorbidities/treatment, and study endpoints will be provided statistical analysis summary.

7.5 Missing data

For participants enrolled in the study, researchers will make every effort to collect their data, especially data related to the primary endpoint. If a participant's efficacy data is missing for any reason, continuous variables will be handled using the last observation carry-forward method (Last Observation Carried Forward, LOCF), while categorical data will be processed according to actual circumstances or filled in through modeling. Missing data. Other processing methods are described in detail in the Statistical Analysis Plan (SAP).

7.6 Statistical analysis methods

7.6.1 Demographic and baseline status, compliance, medical history, and analysis of concomitant disease treatment

Descriptive statistics of demographic and baseline characteristics of enrolled subjects will be performed based on the FAS set. The demographic data and baseline characteristics of all subjects were listed. Descriptive statistics were performed for treatment compliance throughout the study period, and compliance levels were summarized (i.e., <80% Number and percentage of subjects (80% to 120% and >120%). Summarize the number and percentage of subjects with a history of disease and comorbidities/treatment categories.

7.6.2 Statistical analysis of the primary endpoint

Statistical analysis of the primary endpoint will be based on the EAS set, including primary analysis and sensitivity analysis.

1) Main analysis:

1) Descriptive analysis will be used to summarize the baseline, post-treatment 6 months albumin and pre-protein measurements of the subjects in the group, as well as the difference in change from baseline; LOCF will be used to process the data on major efficacy loss

The paired t-test was used to test the difference before and after treatment.

2) Sensitivity analysis: The robustness of the analysis results will be evaluated by considering different missing data processing situations. The missing data of the main efficacy after treatment will be filled with the mean and median of the complete observation data respectively method, hypothesis testing is the same as the main analysis.

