3.3.3 Exit criteria

Participants may withdraw from the study under any circumstances and should withdraw from the study in the following situations:

- (1) The patient developed life-threatening complications;
- (2) The occurrence of intolerable clinical symptoms related to the therapeutic drug;
- (3) Pregnancy was combined during the study;
- (4) The subject was assessed by the investigator as needing to withdraw from the trial;
- (5) Unwilling to continue to participate in the study/informed consent withdrawal;
- (6) Disappearance.

If the subject wishes to discontinue participation in the study, he/she will participate in the termination visit to complete the test items of the termination visit.

4. Research plan

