The daily use of 1 bag of amino acid peritoneal dialysis fluid is during the nighttime sleep period, while the daily use of 2-4 bags of glucose peritoneal dialysis fluid is during the daytime. The total daily infusion volume, each infusion volume, dwell time, and each excretion volume for each subject are adjusted by the researcher based on individual patient conditions and standardized prescriptions. During treatment, subjects should follow the researcher's guidance for daily life and dietary management, and regularly visit the research center for follow-up and examinations. In the third and sixth months of treatment, subjects should repeat the screening period

All evaluation items and any adverse events or serious adverse events are recorded.

The research process is shown in Table 1:

Table 1: Research process table

Evaluate projects	Screening period/baseline	stage of therapy					
		1 month	2 months	3 months	4 months	5 months	6 months
informed consent	√	×	×	×	×	×	×
Inclusion and exclusion criteria	√	×	×	×	×	×	×
Collect demographic data	√	×	×	×	×	×	×
Symptoms (loss of appetite, nausea, vomiting, abdominal distension, Infusion pain, edema, etc.)	√	√	√	√	√	√	√

Previous illness/treatment	✓	✗	✗	✗	✗	✗	✗
Combination therapy with concomitant medication	✓	✓	✓	✓	✓	✓	✓
allergic history	✓	✗	✗	✗	✗	✗	✗
SGA	✓	✓	✓	✓	✓	✓	✓
check-up	✓	✓	✓	✓	✓	✓	✓
vital sign	✓	✓	✓	✓	✓	✓	✓
Ultrafiltration volume	✓	✓	✓	✓	✓	✓	✓
UPD	✓	✓	✓	✓	✓	✓	✓
BMI	✓	✓	✓	✓	✓	✓	✓
CI	✓	✗	✗	✓	✗	✗	✓
skin-fold thickness	✓	✗	✗	✓	✗	✗	✓
Waist circumference and grip strength, upper arm muscle circumference	✓	✗	✗	✓	✗	✗	✓
Hepatitis B related antigen antibody, hepatitis C antibody, HIV antibody	✓	✗	✗	✗	✗	✗	✗
Biochemistry and liver and kidney function (including serum albumin, Prealbumin), glycosylated hemoglobin	✓	✗	✗	✓	✗	✗	✓
White, fasting blood sugar							
Nt-Pro BNP	✓	✗	✗	✓	✗	✗	✓
nPCR	✓	✗	✗	✓	✗	✗	✓

nPNA	✓	✗	✗	✓	✗	✗	✓
Kt/V and Ccr	✓	✗	✗	✓	✗	✗	✓
PET	✓	✗	✗	✓	✗	✗	✓
adverse event	✓	✓	✓	✓	✓	✓	✓

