7.7 Multiplicity issues

This study involves multiple primary efficacy endpoints: Δ serum albumin and Δ prealbumin. If any one of these endpoint indicators is statistically significant, the trial is considered effective, which can lead to an inflated overall false discovery rate (FWER). The Hochberg method is planned to control FWER: the P-values of the two tests are ranked from largest to smallest, denoted as $p(1) > p(2)$, and then compared with the corresponding a_i in descending order. First, the hypothesis $H(01)$ corresponding to the largest r-value $p(1)$ is tested. $\frac{\alpha}{2}$ If $p(1) < a_1$ ($a_1 = a$, one-sided 0.025), all null hypotheses are rejected, and the test is stopped; if the one-sided test $p(1) \geq 0.025$, $H(01)$ is not rejected, and the next test continues; the test level $a_2 =$ (one-sided 0.0125) continues to test $H(02)$. Statistical tests for other indicators are not the primary objective and are not considered multiple adjustments.

8. Ethical norms

The ethical guidelines for this study are as follows:

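### Missing month-6 albumin and prealbumin are carried forward and checked only by mean and median filling, which overstates precision and never lets leavers worsen

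*Combined protocol and SAP*

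**What the plan says.** Section 7.5 states that, for efficacy data missing for any reason, "continuous variables will be handled using the last observation carry-forward method". It leaves other methods to a separate SAP that is not part of the supplied text. Section 7.6.2 repeats the rule for the primary endpoints in the effectiveness analysis set (EAS): "LOCF will be used to process the data on major efficacy loss", followed by a paired t-test of month 6 against baseline.

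The sensitivity analysis reads: "The missing data of the main efficacy after treatment will be filled with the mean and median of the complete observation data respectively", and "hypothesis testing is the same as the main analysis". It does not say whether the month-6 value or the change from baseline is filled.

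This test decides the trial. Section 7.7 says: "If any one of these endpoint indicators is statistically significant, the trial is considered effective". Hochberg's rule tests the larger p-value at one-sided 0.025 and, if that fails, the smaller at 0.0125.

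In Table 1 (Section 4.1), the row "Biochemistry and liver and kidney function (including serum albumin, Prealbumin), glycosylated hemoglobin" is ticked at baseline, month 3 and month 6 only. Reasons for exit in Section 3.3.3 include life-threatening complications and "The occurrence of intolerable clinical symptoms related to the therapeutic drug".

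**The concern.** The value carried forward is normally the month-3 one. It is the baseline value if a patient enters the EAS through another measure, such as the SGA or BMI, which are taken monthly. LOCF gives the right mean 6-month change only if leavers would not, on average, have changed after that value. The design has no control arm in which a similar bias could partly cancel.

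The planned checks do not probe this. LOCF keeps the leaver's own last value, and the fills give leavers the completers' centre. No listed analysis lets leavers decline after their last visit, so agreement among the three would say little about the risk that the exit criteria make foreseeable. The fills also enter invented values into a t-test as if measured, so their p-values are too small even when dropout is purely random.

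**Working it through.** **Inputs.** From Section 7.1: N = 140, of which 112 remain after 20% loss; albumin gain 1.5 g/L, SD 4.5; prealbumin gain 60 mg/L, SD 80; power 0.90; smallest level 0.0125 one-sided. From Section 7.7: levels 0.025 (z = 1.960) and 0.0125 (z = 2.241). Missing shares f of 5, 10 and 20% are assumptions. 20% is an upper figure, because the allowance also covers invalid data and the EAS drops patients with no valid post-treatment data.

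**Plan's own figures.** n = ((2.241 + 1.282) × SD/gain)² gives 111.7, so 112, for albumin and 22.1, so 23, for prealbumin; 112/0.8 = 140. All three reproduce.

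**1. Single filling under random dropout with no effect.** If the change is filled by the mean, the estimate is the completers' mean, with true SE SD/√(N(1−f)). The t-test uses an SE smaller by a factor of about 1−f (0.340 against 0.425 g/L at 20%). Actual error = 1 − Φ(1.960 × (1−f)):

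| Missing | Formula | Change filled, overall range | Month-6 value filled, simulated |
|---|---|---|---|
| 5% | 3.1% | 3.0–3.5% | 2.8–3.0% |
| 10% | 3.9% | 3.7–4.1% | 3.0–3.3% |
| 20% | 5.8% | 5.7–6.1% | 3.7–4.4% |

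The ranges cover mean and median filling and assumed between-visit correlations of 0.5 to 0.8.

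**2. LOCF bias** = f × (mean further change that went unobserved).
- Leavers lose 1.5 g/L after month 3 (assumption): the mean is overstated by 0.075, 0.15 and 0.30 g/L at 5, 10 and 20%.
- Steady rise, 0.75 g/L at month 3 and 1.5 at month 6 (assumption): the mean is understated. At 20% it is 1.5 − 0.2 × 0.75 = 1.35.
- Baseline carried forward: the change is set to zero, which understates any gain.

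**3. LOCF and trial-level error.** Assume an albumin gain of 0.75 g/L at month 3 that is gone by month 6, random dropout, prealbumin null, and independent endpoints. The albumin statistic shifts by f × 0.75/(4.5/√140) = 0.099, 0.197 and 0.394. Let A and A′ be its chances of passing 0.0125 and 0.025. Prealbumin's chance of falling between those levels is 0.0125, so Hochberg declares success with probability A + 0.0125 − 0.0125A + 0.0125(A′ − A).
- 5%: A = 0.0161, A′ = 0.0313; total 2.9%.
- 10%: A = 0.0205, A′ = 0.0390; total 3.3%.
- 20%: A = 0.0324, A′ = 0.0587; total 4.5%.

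Simulation gave 2.6–3.1%, 3.1–3.4% and 4.4%. With zero change at both visits, the single LOCF test stayed at 2.3–2.7% against a nominal 2.5%.

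**4. Tipping point.** Let delta be how much worse leavers are than completers at month 6. Significance is lost at delta = (gain − z × SD/√completers)/f. At 20% missing the albumin SE is 4.5/√112 = 0.425:

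| Observed gain | Level 0.025 | Level 0.0125 |
|---|---|---|
| Albumin 1.5 g/L | (1.5 − 0.833)/0.2 = 3.3 | (1.5 − 0.953)/0.2 = 2.7 |
| Albumin 1.2 g/L | (1.2 − 0.833)/0.2 = 1.8 | (1.2 − 0.953)/0.2 = 1.2 |
| Prealbumin 60 mg/L | (60 − 14.8)/0.2 = 226 | (60 − 16.9)/0.2 = 215 |

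The 0.025 column applies to albumin when prealbumin is also significant with the smaller p-value; the 0.0125 column applies when albumin must carry the trial alone. At level 0.0125 and 5 and 10% missing, albumin (gain 1.5) tips at 12.5 and 6.0 g/L.

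**5. Direction of the checks.** Assume everyone gains 0.6 g/L by month 3, completers reach 1.2 at month 6, the 20% missing would have returned to 0, and baselines are similar. The true mean is 0.8 × 1.2 = 0.96. LOCF gives 0.96 + 0.2 × 0.6 = 1.08. Both fills give about 1.20, further from the truth than the analysis they check.

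**The case against.** A fair defence has five parts.

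- **Robust at planning values.** This stands. The tipping points are large, above all for prealbumin, and one significant endpoint suffices. If prealbumin passes 0.0125, the success call survives whatever happens to albumin.
- **The error of the deciding test.** A reader might infer a false-positive rate of 5.9% from the albumin test at 0.025 in step 3. The documents do not support that as the trial's error: Section 7.7 lets albumin succeed at 0.025 only if prealbumin also passes 0.025, and otherwise requires 0.0125. Even the 4.4% rests on an assumed transient gain. Calling it an error also rests on the month-6 reading in Sections 7.1 and 7.6.2, whereas Section 3.2.1 names month 3 as well.
- **LOCF is not always favourable.** This stands: it can understate benefit, and the documents give no expected decline after month 3.
- **The fills do not decide the trial, and may be stricter than LOCF.** This stands in part. In the step 5 example, filling the month-6 value by the mean was significant at 0.0125 in 67–78% of simulated trials, LOCF in 71–72%, and the full true data in 60%. Filling the change reached 84%.
- **A mixed model does not cure unobserved worsening.** This stands. It would report about 1.20 in step 5, against 1.08 for LOCF.

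The absent SAP may also contain more. None of this supplies, in the text at hand, an analysis in which leavers worsen, or removes the overstated precision of the fills.

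**Conclusion.** The point holds as a weakness that should be fixed, not as proof that the primary result would be wrong. Two parts rest on the text and simple algebra: the fills overstate precision (5.7–6.1% for a nominal 2.5% at 20% missing if the change is filled, less otherwise), and no supplied analysis lets leavers worsen. The size of any LOCF bias depends on an unknown further change and can have either sign. Under the assumed transient albumin gain, the trial-level error is about 2.6–3.1%, 3.1–3.4% and 4.4% at 5, 10 and 20% missing.

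The practical exposure is an albumin gain smaller than planned. At 1.2 g/L and 20% missing, significance goes if leavers are 1.8 g/L worse than completers, or 1.2 g/L if albumin must stand alone. A gain below plan is realistic, since the protocol's own background section cites a meta-analysis that found the albumin effect uncertain. A reader might infer that LOCF generally favours treatment or that the prealbumin conclusion is fragile; neither follows.

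**What to change.** - **Section 7.6.2, sensitivity analysis.** Replace mean and median filling with multiple imputation plus a prespecified delta-adjusted (tipping-point) analysis for both endpoints. Raise delta until significance at the applicable Hochberg level is lost, and report that delta. Do not cap it at, say, 3 g/L or 120 mg/L: most of the tipping points above lie beyond those limits.
- **Sections 7.5 and 7.6.2, primary analysis.** A mixed model for repeated measures on the baseline, month-3 and month-6 data is a reasonable replacement for LOCF, testing month 6 minus baseline and keeping the Hochberg step. It is unbiased for the month-6 change under missing at random. In the random-dropout setting of step 3, its single-test error was 2.2–2.6% for a nominal 2.5%. Unobserved worsening must be covered by the delta analysis.

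**Cost.** A little more programming on data already scheduled, with no extra visits or patients. The mixed model's standard error is about 2%, 4% and 8–9% larger than LOCF's at 5, 10 and 20% missing (0.39, 0.40 and 0.41 against 0.38 g/L).
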